- *Muscle weakness*: difficulty walking or getting up from a chair, grabbing things or carrying things with the hands as a result of muscle weakness from nerve damage
- *Balance problems*: increased unsteadiness and incoordination when walking, occurring as the body adapts to changes brought on by muscle damage
- *Serious foot problems*: such as ulcers, infections, deformities, and bone and joint pain

➤ Complications: Diabetic neuropathy can cause numerous serious complications. Among the most serious are the following two complications:

- *Loss of a limb*: As nerve damage can cause lack of feeling in the feet, cuts and sores can go unnoticed and eventually become severely infected or ulcerated. The risk of infection is high because diabetes reduces blood flow to the feet. Infections that spread to the bone and cause tissue death (gangrene) may be impossible to treat and require amputation of a toe, foot or even the lower leg. More than half the non-traumatic lower limb amputations performed every year in the United States are due to diabetes.
- *Charcot joint*: This occurs when a joint, usually in the foot, deteriorates because of nerve damage. Charcot joint is marked by loss of sensation, as well as swelling, instability and sometimes deformity in the joint itself.
- *Neuropathic pain* is difficult to control and can seriously affect emotional well-being and overall quality of life. Neuropathic pain is often worse at night, seriously disrupting sleep and adding to the emotional burden of sensory nerve damage.

DIAGNOSIS

Patients being evaluated for diabetic peripheral neuropathy will have already been clinically diagnosed with diabetes and/or be evaluated for and diagnosed with diabetes prior to the evaluation for diabetic peripheral neuropathy.

Diabetic neuropathy is diagnosed by a qualified physician based on a thorough evaluation of the patient's symptoms, medical history and a physical exam that includes

assessment of blood pressure, heart rate, muscle strength and tone, tendon reflexes, and sensitivity to touch, position changes, temperature and vibration.

A comprehensive foot exam assessing the skin, muscles, bones, circulation, and sensation of the feet is also performed as part of the diagnostic process.

Specific tests that may be conducted as part of the diagnostic process include:

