Final sample size = $29 \times 1/(1-0.083)$

Final sample size = $29 \times 1/0.917 = 29 \times 1.0905 = 31.62$, rounded to 32 subjects per procedure group.

Therefore, a minimum starting sample size of 32 subjects in each group is needed to ensure that sufficient numbers remains at the end of the trial (29 subjects per group) for any significant differences found between groups to be considered statistically valid and representative of the general population being sampled. This results in a total of 64 subjects being enrolled in this study across both study procedure groups.

Recruitment

Subjects will be recruited from among the Principal Investigator's/test site's pool of patients who are currently being treated for, or who are seeking treatment for, diagnosed diabetic peripheral neuropathy, or from response to the following recruitment materials.

a) Flyer

WANTED

**ADULTS WITH DIABETES WITH FOOT PAIN
ONGOING OVER THE LAST 3 MONTHS FOR**

A

**CLINICAL STUDY OF THE EFFECTS OF
LOW LEVEL LASER LIGHT ON
REDUCING FOOT PAIN**

**THIS STUDY INVOLVES TWELVE
LASER LIGHT PROCEDURES
WITH THE ERCHONIA® FX-635™ LASER
OVER SIX WEEKS AT THE TEST SITE.**

**THERE ARE THREE MORE VISITS TO THE TEST SITE
TWO WEEKS, FOUR WEEKS AND THREE MONTHS
AFTER THE LAST LASER LIGHT PROCEDURE.**

FOR MORE INFORMATION PLEASE

CONTACT:

<PI name>
<test site name & location>
<phone # and/or e-mail>

b) Newspaper Ad

Diabetic Foot Pain Research Study

This study is to see if the Erchonia® FX-635™, a non-invasive, investigational device that uses low-level laser light, can help to relieve foot pain in people with diabetes that has been ongoing for at least 3 months.

The study involves fifteen visits to a test site and recording some information at home.

Please contact <PI name> at <test site name & location> at <phone and/or e-mail> for details.

Compensation

A subject will not receive financial or any other form of compensation to participate in this clinical study. However, he or she will also not be charged for the cost of the study procedures with the Erchonia® FX-635™ Laser or for the cost of any other directly-related evaluations or measurements that occur as part of his or her participation in the study.

STUDY PROCEDURE

STUDY TEST BATTERY

The following is a list of the study outcome assessment tools that will be used in this clinical study. For each study phase, the precise tools from this list that will be employed will be specified.

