changes are reported, the investigator will review the change(s) to determine if the subject continues to qualify for study participation.

PRE-PROCEDURE VARIABLES

The following pre-procedure variables will be recorded prior to commencement of the procedure administration phase (prior to procedure administration #1), as listed and described in the STUDY TEST BATTERY section above.

- Baseline Foot Variables
- Baseline Concomitant Medication and Therapy Use
- Subject Demographics

PRE-PROCEDURE MEASURES

The following pre-procedure measures will be recorded prior to commencement of the procedure administration phase (prior to procedure administration #1), as listed and described, and according to the methodology outlined, in the STUDY TEST BATTERY section above.

- Visual Analog Scale (VAS) Degree of Pain Rating
- Neuropathic Pain Symptom Inventory (NPSI)

PROCEDURE ADMINISTRATION PHASE

PROCEDURE ADMINISTRATION PROTOCOL

- The procedure administration phase of the study commences within one hour subsequent to recording of the pre-procedure measures and variables, on the same day.
- The procedure administration phase extends over 6 consecutive weeks.
- Each subject receives 12 total procedure administrations with the Erchonia® FX-635™ across the consecutive 6-week procedure administration phase, 2 procedure administrations per week, each procedure administration approximately evenly spaced. That is, each procedure administration will be 3 or 4 days apart with a treatment window of ±1 day.
- Each procedure administration lasts a total of 15 minutes per foot, for a total combined procedure administration time of 30 minutes per session.
- Each procedure administration with the Erchonia® FX-635™ is administered at the investigator's test site.
- The procedure administration protocol for each session is as follows:
 1. The subject enters the procedure administration room and is seated on a chair with the right foot elevated.
 2. The subject is correctly fitted with the laser safety glasses.
 3. The procedure administrator puts on the laser safety glasses and selects the Erchonia® FX-635™ Laser A or B according to the subject's procedure group assignment.
 4. The FX-635™ Laser is positioned around the foot such that each of the 3 laser lights is positioned between 3 and 4 inches away from, but directed toward, a) the top of the foot (dorsal aspect); b) the bottom of the foot (plantar aspect); and c) the posterior tibial nerve within the tarsal tunnel.

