 5. The FX-635™ Laser is activated
 6. The laser diodes laze each of these 3 areas for 15 minutes simultaneously.
 7. The procedures listed in 4. through 6. above is repeated for the left foot.
 8. The investigator and the subject remove the safety glasses.
 9. The subject rises and leaves the procedure administration room.

At each of the procedure administration test site visits, the investigator performs an adverse events evaluation.

PROCEDURE ADMINISTRATION PHASE MEASURES

DAILY MEASURES

Commencing on the same day as the first study procedure administration with the Erchonia® FX-635™ is administered, the subject will begin to record the required information in the Subject Daily Diary, as applicable, at home.

FOLLOWING EACH PROCEDURE ADMINISTRATION

Within 10 minutes following administration of each of the first 11 study procedure administrations with the Erchonia® FX-635™, the subject will record the following at the test site:

- Visual Analog Scale (VAS) Degree of Foot Pain Rating
- Adverse Events Evaluation

POST-PROCEDURE ACTIVITIES

POST-PROCEDURE EVALUATION PHASE

The post-procedure administration evaluation phase of this study will commence immediately following completion of the procedure administration phase and will last 3 months (about 12 weeks).

POST-PROCEDURE EVALUATION VISITS AND MEASURES

There will be 4 post-procedure evaluation visits. The first post-procedure evaluation visit will occur at the test site, and the remaining three post-procedure evaluation visits will take place at the subject's home. The subject will be provided with pre-dated case report forms on which to record the required information on each of those three post-procedure days, and a staff member at the investigator's test site will contact the individual on the designated day to remind him or her to record the required information. These visits, and the associated measures to be recorded at each visit, as listed and described, and according to the methodology outlined, in the STUDY TEST BATTERY section above are as follows:

DAILY MEASURES: AT HOME

The subject will continue to record the required information in the Subject Daily Diary, as applicable, at home, through to the 4 weeks post-procedure evaluation visit.

STUDY ENDPOINT EVALUATION: FOLLOWING COMPLETION OF THE PROCEDURE ADMINISTRATION PHASE: AT THE TEST SITE

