At each evaluation and procedure administration test site visit throughout the clinical study, and at any other time throughout the duration of the clinical trial that is necessary, evaluation for the occurrence of any potential adverse event will occur. This includes any observations made by the study investigator or other study staff or any reports made by the subject. Subjects will be instructed as to what constitutes an adverse event and how to report any potential adverse event(s) he or she may identify during study participation to the test site. The subject will be instructed to formally evaluate for potential adverse events through their recordings in their Subject Daily Diary completed at home.

RECORDING OF ADVERSE EVENTS

AEs that occur after randomization are recorded by the Principal Investigator on the AE page of the CRF. Recording is done in a concise manner using standard, acceptable medical terms. Any clinically significant changes in pre-existing conditions (based on medical history/physical examination results) are recorded on the CRF AE pages.

REPORTING OF ADVERSE EVENTS

The investigator will notify the Sponsor right away of any identified or reported adverse event, whether determined by the investigator to be related or unrelated to the study treatment or device or whether it is an anticipated or unanticipated AE. The investigator and the Sponsor will determine if the AE is a promptly reportable event to the governing IRB. The investigator will formally report any serious, life-threatening, or unexpected adverse experiences, including death that occurs within the duration of this study regardless of the relationship to the study procedure.

PROTOCOL DEVIATIONS AND VIOLATIONS

Both protocol deviations and protocol violations are accidental or unintentional changes to, or non-compliances with, the IRB-approved research protocol without prior sponsor and IRB approval. The difference between the two lies in the level of risk introduced by the change.

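### Recruitment texts place the 2-week, 4-week and 3-month follow-ups at the test site but the procedure places them at home; if the procedure governs, no on-site adverse event evaluation is scheduled for about the last 12 of 18 weeks

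*Combined protocol and SAP*

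**What the plan says.** **Recruitment texts.** Under Recruitment, the flyer tells candidates "THERE ARE THREE MORE VISITS TO THE TEST SITE" and gives the timing, counted from the last laser procedure, as "TWO WEEKS, FOUR WEEKS AND THREE MONTHS". The newspaper ad states: "The study involves fifteen visits to a test site and recording some information at home".

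**Procedure.** Under Post-Procedure Evaluation Visits and Measures: "The first post-procedure evaluation visit will occur at the test site, and the remaining three post-procedure evaluation visits will take place at the"; the location that completes this sentence is the home of the subject. The subject fills in pre-dated forms on those three days, and a staff member makes contact on the day "to remind him or her to record the required information". The headings of the three follow-up evaluations and the Table of Subject Events both mark them as taking place at home. An AE evaluation is listed at each.

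**Adverse events.** During treatment the investigator evaluates AEs at every procedure visit. The one on-site post-procedure evaluation takes place within ten minutes of the twelfth procedure. Evaluation of Adverse Events schedules assessment "At each evaluation and procedure administration test site visit throughout the clinical study" and also whenever else in the trial it is needed. It says that subjects are taught what an AE is and how to report one, and that they use the Subject Daily Diary for this at home. The diary covers ten weeks, ending four weeks after the last procedure. The Principal Investigator records AEs on the case report form (CRF), and the investigator notifies the Sponsor without delay.

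**The concern.** Two problems share one source.

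First, a text shown to candidates disagrees with the procedure about where three evaluations take place. Both cannot be right, and the protocol asks the Principal Investigator to stress the number and frequency of visits at consent.

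Second, the location decides how AEs are found. At the site, an investigator evaluates. At home, under the procedure as written, the subject evaluates and a staff member only reminds. The population makes this matter. The Complications text under Presentation and Symptoms warns that with lost feeling in the feet "cuts and sores can go unnoticed and eventually become severely infected or ulcerated". The protocol's list of potential AEs includes infection, discoloring and indentations, which a person with reduced sensation may miss if the feet are not looked at. The safety analysis compares the percentage of subjects with AEs between arms, so incomplete late capture would make that comparison less informative about the follow-up period.

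**Working it through.** **Step 1: reproduce the ad's visit count.** The Procedure Administration Protocol states: "Each subject receives 12 total procedure administrations with the Erchonia® FX-635™ across the consecutive 6-week procedure administration phase". The flyer adds 3 site visits.

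- Sessions + flyer follow-ups = 12 + 3 = 15, the ad's figure.

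**Step 2: count site visits under the procedure section.** The Day 1 evaluation falls on the day of session 1 and the endpoint evaluation on the day of session 12, so neither adds a visit.

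- Sessions only, three follow-ups at home = 12.
- With a separate qualification visit = 12 + 1 = 13.

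Neither equals 15. The match in Step 1 leaves out a qualification visit; counting one would give 12 + 3 + 1 = 16. The ad's number therefore fits the flyer's version but does not prove it.

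**Step 3: time without a scheduled on-site AE evaluation, if the procedure section governs.** Treatment lasts 6 weeks and the post-procedure phase 3 months, which the protocol equates to about 12 weeks. The last on-site evaluation is at the start of that phase.

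- Total = 6 + 12 = 18 weeks.
- Share = 12 / 18 = 67%.
- Taking 3 months as 13 weeks: 13 / (6 + 13) = 13 / 19 = 68%.
- Post-procedure AE evaluations: 1 at site, 3 at home; 3 / 4 = 75% at home.

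**Step 4: what is captured in those weeks.**

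- Diary = 6 + 4 = 10 weeks, so AEs are still recorded daily for the first 4 weeks after the last procedure.
- Weeks after the diary ends = 18 - 10 = 8; 8 / 18 = 44%.
- With 13 weeks of follow-up: 13 - 4 = 9 weeks.
- Scheduled AE capture in that stretch: the one home form at three months.

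**Step 5: the other version.** If the flyer governs, there are three on-site visits after session 12, and the Evaluation of Adverse Events section attaches an evaluation to each. The gap in Step 3 then closes, but the post-procedure section and the events table are wrong.

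**The case against.** The strongest reply is that safety follow-up does not stop when site visits do, and this is correct. AE evaluations are listed at all three home time points, staff contact the subject on each of those days, the diary runs to week 4, and subjects are instructed in reporting. The general rule also allows evaluation at any time it is needed. A reader might infer that late safety data rest on unprompted self-report. The documents do not support that, and the home forms, which may prompt for specific events, are in an appendix that is not available.

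A reader might also infer that no clinician ever assesses a late event. That too goes beyond the text: the Principal Investigator records any AE, the investigator judges relatedness and notifies the Sponsor, and nothing limits this to events found on site. What is missing is a scheduled on-site evaluation.

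Nor do the documents show that under-reporting will occur or that it would bias the comparison between arms. Sensory loss is not an entry criterion, several listed AEs are visible, and both arms follow the same schedule.

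Finally, only the flyer contradicts the procedure in words. The ad names no follow-up time points, and the consent form, which is said to detail the commitment, is not available. So it cannot be said that enrolled subjects will expect visits that do not happen.

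What stands after all this is the conflict over location and, under the procedure section, the long interval with self-recorded AEs only.

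**Conclusion.** The contradiction is explicit and should be resolved. The safety point holds conditionally: if the procedure section governs, about 12 of 18 weeks (67%) have no scheduled on-site AE evaluation, and the last 8 weeks or so have a single home form as the only scheduled capture. This rests on the protocol's own equation of 3 months with about 12 weeks; a 13-week reading changes little.

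Late foot events may be under-reported, on the strength of the protocol's own statement about unnoticed sores. The documents give no rate from which to estimate how many, and no ground for expecting a difference between arms. The primary endpoint is not touched, because it is recorded at the site after session 12. The open-label site visits do not fill the gap: they come after the 18 weeks and involve only placebo subjects who choose to take part.

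**What to change.** 1. Make the flyer, the newspaper ad, the post-procedure section with its follow-up headings, and the Table of Subject Events agree on where the three follow-ups take place, and correct the ad's visit count to match.
2. If follow-up stays at home, use the contact staff already make on each designated day to ask about every event on the protocol's list of potential AEs and about any new skin change or wound on the feet since the last contact, including whether the feet were looked at. Record the answers on the AE CRF that day and pass any positive answer to the investigator through the existing reporting route.
3. Amend Evaluation of Adverse Events so that scheduled evaluation covers these home contacts as well as test-site visits.

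The cost is a short script, a few more minutes per contact, and an amendment to the protocol and recruitment texts with the approval that requires. No new visit or staff is needed. Recorded AE counts may rise in both arms. The change has limits: it is still self-report, it adds no contact between week 4 and month 3, and it does not replace an examination.

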- APPENDIX B: PI INSTRUCTIONS FOR VAS MEASUREMENTS
- APPENDIX C: NPSI & RELATED JOURNAL ARTICLES
- APPENDIX D: CASE REPORT FORMS

STUDY INFORMATION

SPONSOR

Erchonia Corporation
[name]
[name]
Contact: [name], President
[contact]
E-mail: [contact]

REGULATORY CONSULTANT

Regulatory Insight, Inc., Denver Office
[name]
[name]
Contact: [name], Principal Consultant
[contact]
E-mail: [contact]

CLINICAL CONSULTANT

Regulatory Insight, Inc., Nashville Office
[name]
[name]
Contact: [name], Clinical Consultant
[contact]
E-mail: [contact]

MONITOR

Erchonia Corporation
[name]
[name]
Contact: [name]
[contact]
E-mail: [contact]

PRINCIPAL CLINICAL INVESTIGATORS AND TEST SITES

- [name], DPM, MS
Hialeah Hospital Medical Plaza
[name]
[name]
[contact]
e-mail: [contact]
IRB Study Number: 1251019

- [name], DPM
Pensacola Podiatry, P.A.
[name]
[name]
[contact]
e-mail: [contact]

INSTITUTIONAL REVIEW BOARD

Western Institutional Review Board® (WIRB®)

[name]

[name]

[contact]

e-mail: [contact]

IRB Tracking No. : 20150254

PURPOSE OF STUDY

The purpose of this clinical study is to determine the effectiveness of the Erchonia® FX-635™, manufactured by Erchonia Corporation (the Company), in providing relief of foot pain in individuals with chronic painful diabetic peripheral neuropathy.

INDICATION FOR USE

The indication (claim) being sought through support of the results of this clinical study is: "The Erchonia® FX-635™ is indicated for adjunctive use in providing relief of chronic pain arising from diabetic peripheral neuropathy."

It is intended that the results of this clinical study be used to support a 510(k) submission to FDA for clearance to market the device for the intended indication.

EXPECTED RESULTS

Following completion of the study procedure protocol with the Erchonia® FX-635™ relative to baseline, it is anticipated that significantly more subjects in the test group than in the placebo group will show a 30% or greater reduction in self-reported VAS pain rating in the feet.

RESOURCES

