BASELINE FOOT VARIABLES: The following is recorded at baseline evaluation:

- (i) Duration of Pain: years/months since foot pain began
- (ii) Number of Months/Years Since Diabetes Diagnosis
- (iii) Insulin Dependency: Insulin dependent diabetes or non-insulin dependent diabetes

BASELINE CONCOMITANT MEDICATION AND THERAPY USE: The following is recorded at baseline evaluation:

- (i) Over-the-counter and prescription medications that have been used specifically to relieve the subject's diabetic peripheral neuropathy foot pain, presently or in the past.
- (ii) Non-drug treatments/therapies (conventional, alternative, experimental and recreational/medicinal) that have been used specifically to relieve the subject's diabetic peripheral neuropathy foot pain, presently or in the past.
- (iii) Over-the-counter and prescription medications currently used, and therapies currently engaged in by the subject for any non-pain relief indication, including dosages, frequency of use and indication for use.

SUBJECT DEMOGRAPHICS: The subject's age and gender are recorded.

VISUAL ANALOG SCALE (VAS) DEGREE OF PAIN RATING: Subjects will be asked to rate the overall degree of pain experienced in their feet on the following 0-100 mm (0 - 10 cm) Visual Analog Pain Scale, by responding to the following question:

"Using the scale below, please mark with a cross (X) the spot along the 0 to 100 line below that best shows **how much pain you feel in your feet** right now. '0' means you feel no pain at all and '100' means you feel the worst pain imaginable. **Please mark only one spot. Do not think of or write in a number.**"

The Visual Analog Pain Scale (VAS) is one of the three most commonly used scales for assessing chronic pain. It is a simple scale that consists of a line anchored at one end by a label such as "NO PAIN" and at the other end "WORST POSSIBLE PAIN". The subject marks on the line the spot for the pain intensity, which is then measured.

Standard guidelines for effective use of the VAS that are followed in this clinical study are:

- i. The line should be 10, 15 or 20cm long, as other lengths are less reliable.
- ii. There should be a small vertical mark at each end, with numbers 0 and 100, and a verbal description.
- iii. The verbal description must be in absolute terms (e.g. worst pain imaginable);

- iv. The line itself should be clear of any markings and should be horizontal rather than vertical, for more reliable measurements.

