The study endpoint evaluation visit will occur at the test site within ten minutes following completion of the procedure administration phase, after administration of the 12th and final procedure administration with the Erchonia® FX-635™.

The following measures will be recorded at this visit:

- Visual Analog Scale (VAS) Degree of Foot Pain Rating
- Neuropathic Pain Symptom Inventory (NPSI)
- Subject Satisfaction With Foot Pain Level
- Subject Perceived Group Allocation and Rationale
- Assessment Investigator Perceived Group Allocation and Rationale
- Adverse Events Evaluation

TWO WEEKS POST-PROCEDURE EVALUATION: AT HOME

Two weeks following completion of the procedure administration phase, the following measures will be recorded:

- Visual Analog Scale (VAS) Degree of Pain Rating
- Adverse Events Evaluation

FOUR WEEKS POST-PROCEDURE EVALUATION: AT HOME

Four weeks following completion of the procedure administration phase, the following measures will be recorded:

- Visual Analog Scale (VAS) Degree of Pain Rating
- Neuropathic Pain Symptom Inventory (NPSI)
- Subject Satisfaction With Foot Pain Level
- Adverse Events Evaluation

THREE MONTHS POST-PROCEDURE EVALUATION: AT HOME

Three months following completion of the procedure administration phase, the following measures will be recorded:

- Visual Analog Scale (VAS) Degree of Pain Rating
- Neuropathic Pain Symptom Inventory (NPSI)
- Subject Satisfaction With Foot Pain Level
- Adverse Events Evaluation

OPEN-LABEL PLACEBO SUBJECT PROCEDURE ADMINISTRATION PERIOD

Following completion of the 3-month post-procedure administration phase, individual subject blinding will be broken. Subjects who had been randomized to the placebo (sham) procedure group will then be offered participation in an additional 6-week post-study open-label procedure administration period during which time they will knowingly receive the active 6-week 12-procedure administration protocol with the Erchonia® FX-635™ Laser as did the subjects initially assigned to the active test procedure group at the time of study enrollment.

Participation in the 6-week post-study open-label procedure administration period is voluntary for subjects who had been assigned to the placebo (sham) procedure group. Participation in the 6-week post-study open-label procedure administration period will not be offered to subjects who had initially been randomized to the active test laser procedure group.

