6. K041139; 09/30/04: "The Erchonia EML Laser is indicated as an adjunct to liposuction procedures of the thighs, hips and stomach for reduction of pain associated with the recovery process."

Evaluation Time Point

The study end evaluation time point at which primary study success will be analyzed is at six weeks post-baseline, following completion of the 12th and final study procedure administration with the Erchonia® FX-635™.

Null Hypothesis: There will be no statistically significant difference in the proportion of individual successes, as defined, between the test and control groups.

Alternative Hypothesis: There will be a statistically significant difference in the proportion of individual successes, as defined, between the test and control groups, to the effect of 35% or greater.

SECONDARY EFFICACY OUTCOME MEASURES

Secondary efficacy outcome measures will be evaluated for the following four data sets:

1. The blinded data set only attained from subjects who were initially enrolled in either the test or placebo procedure group and will not include active procedure test data attained from placebo subjects who partook in the post-study open-label procedure administration period after blinding was broken.

For this group, the following secondary efficacy outcome measure will be evaluated:

- a) Change in VAS rating across and between all study evaluation time points within and between treatment groups
 - b) Change in scores on the Neuropathic Pain Symptom Inventory (NPSI) across and between all evaluation points within and between treatment groups
 - c) Differences in the use of rescue pain medication between procedure groups across study duration
2. The combined data set comprising the blinded data set attained from subjects who were initially enrolled in either the test or placebo procedure group, and the active procedure test data attained from placebo subjects who partook in the post-study open-label procedure administration period after blinding was broken, comparing combined test (blinded and non-blinded) to placebo data

For this group, the following secondary efficacy outcome measure will be evaluated:

- a) Change in VAS rating across and between all study evaluation time points to study endpoint evaluation within and between treatment groups
- b) Changes in scores on the Neuropathic Pain Symptom Inventory (NPSI) across and between all evaluation points to study endpoint evaluation within and between treatment groups

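### Primary success alone does not separate a short-lived post-session effect from relief of chronic pain, and the off-session ratings that could help are under-specified

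*Combined protocol and SAP*

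**What the plan says.** The claim (Indication for Use) is that the device is "indicated for adjunctive use in providing relief of chronic pain arising from diabetic peripheral neuropathy". It carries no limit to temporary relief, although some of the sponsor's earlier clearances listed under Resources do.

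The primary instrument (Study Test Battery, VAS) is momentary. The subject marks the pain felt in the feet "right now. '0' means you feel no pain at all and '100' means you feel the worst pain imaginable".

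The primary time point (Evaluation Time Point) is "at six weeks post-baseline, following completion of the 12th and final study procedure administration". The Study Endpoint Evaluation section places that visit "within ten minutes following completion of the procedure administration phase", that is, after session 12.

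At each session (Procedure Administration Protocol) the subject "is seated on a chair with the right foot elevated". The left foot is then treated in the same way, "for a total combined procedure administration time of 30 minutes per session". Sham subjects follow the same procedure.

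The other on-treatment ratings are also post-session: "Within 10 minutes following administration of each of the first 11 study procedure administrations". The only VAS before a session is the Day 1 pre-procedure rating. The Subject Daily Diary, kept for 10 weeks, has no pain score.

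After the course, VAS is rated at home at 2 weeks, 4 weeks and 3 months. Individual blinding is broken only after the 3-month phase. Secondary outcome 1(a) compares change in VAS within and between groups at all time points in the blinded data set, with ANCOVA for continuous measures. The 30% rule and the 35-point success criterion apply at study endpoint only. Missing data are handled by last observation carried forward (LOCF).

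**The concern.** The result that decides the trial is one mark of current pain, made minutes after half an hour of treatment. A device that eased pain for an hour after each session and did nothing otherwise could meet the criterion. So could one that gave lasting relief. The claim concerns chronic pain, so the difference matters to anyone reading a positive result.

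The protocol accepts this logic elsewhere. Under Rescue Pain Medication Use it holds back a VAS until the effect of rescue medication has worn off, because a recent short-acting influence would colour a momentary rating.

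The off-session evidence is there, but it is loosely specified. The reader will want to know whether the responder difference seen minutes after session 12 is also seen away from a session, and no analysis is planned to answer that on the same scale.

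**Working it through.** **1. VAS ratings set against the sessions**

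| Ratings | Number | Place | Relation to a session | Use in the plan |
|---|---|---|---|---|
| Two washout days | 2 | Home | Before any session | Qualification |
| Day 1, pre-procedure | 1 | Site | Session 1 starts within one hour | Pre-treatment measure |
| Sessions 1 to 11 | 11 | Site | Within 10 minutes after | Change in VAS |
| Session 12 | 1 | Site | Within 10 minutes after | Primary: 30% responder and ANCOVA |
| 2 weeks, 4 weeks, 3 months | 3 | Home | No session | Change in VAS only |

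The total is 2 + 1 + 11 + 1 + 3 = 18. From the first session to the last there are 11 + 1 = 12 ratings, all post-session. The three ratings clear of a session after treatment begins all fall after the course has ended.

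**2. What the three home ratings can and cannot show**

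- A between-group difference at 2 weeks or later cannot be a ten-minute effect. That would be direct, blinded evidence of persistence.
- No difference at 2 weeks has two readings: the effect never outlasted a session, or it was sustained during treatment and faded afterwards. Only an off-session rating during the treatment weeks separates them, and after Day 1 there is none.

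**3. LOCF**

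If the 2-week rating is missing, the last observation is the mark made after session 12. If all three home ratings are missing, that mark fills all three. A subject who leaves during treatment carries an earlier post-session mark forward. The plan enrols 32 per arm to keep 29, so its own allowance is 32 − 29 = 3 per arm, or 3/32 = 9.4%. At that allowance, carried values could move an arm's off-session responder proportion by at most 9.4 percentage points. More missing home forms would raise that limit.

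**4. NPSI at the endpoint visit**

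Its recall is 24 hours, or 1,440 minutes. The session and the ten-minute window take up to 30 + 10 = 40 minutes. So about (1,440 − 40)/1,440 = 97% of the recall period precedes session 12, although the form is answered just after it.

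**5. Sample size**

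The plan's figure reproduces. With 55% versus 20%, mean 0.375, two-sided 0.05 and 80% power:

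n = [1.96 × √(2 × 0.375 × 0.625) + 0.842 × √(0.55 × 0.45 + 0.20 × 0.80)]² / 0.35² = (1.342 + 0.537)² / 0.1225 = 28.8, so 29 per arm.

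Those rates are stated for the change from baseline to study endpoint. The documents give none for an off-session rating. Holding placebo at 20% and varying the active rate (assumptions), exact Fisher power at 32 per arm is:

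| Active rate off-session (assumed) | Power |
|---|---|
| 55% | 0.78 |
| 50% | 0.64 |
| 45% | 0.49 |
| 40% | 0.33 |
| 30% | 0.10 |

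The 95% half-width for the difference at 40% versus 20% is 1.96 × √((0.40 × 0.60 + 0.20 × 0.80)/32) = 1.96 × 0.112 = 0.22, or about 22 percentage points. Off-session responder comparisons in this trial should therefore be read as estimates with intervals, not as pass-or-fail tests.

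**The case against.** The best counter-argument is that the trial already addresses durability. Three blinded home ratings are compared between groups, mean change answers the persistence question as well as a responder rate does, and the NPSI at the endpoint visit looks back over a day. This is largely right. A reader might infer that the trial as a whole cannot tell a brief effect from chronic relief; the documents do not support that. The limit belongs to the primary criterion.

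Three other stronger readings also fail:

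- **That rest biases the result.** Both arms sit through the same 30-minute session and are rated at the same moment, so the between-group comparison is protected.
- **That rest and expectation push response above the planned 20%.** That rate was set for this same post-session rating in a sham arm with the same session. Nothing shows that it leaves out rest or expectation.
- **That the immediate effect is wholly unmeasured for want of a pre-session rating.** The Day 1 marks before and after session 1, in both randomised arms, estimate the immediate change over one session. What is missing is the same information later in the course.

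What the counter-argument leaves standing is narrower: no responder analysis off-session, LOCF that can import a post-session mark into a home time point, and no on-treatment off-session VAS after Day 1.

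**Conclusion.** The point holds as one of interpretation, not validity. Primary success by itself does not distinguish a short post-session effect from relief of chronic pain. Other blinded ratings bear on the question, but as planned they answer it incompletely.

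The size of a post-session effect at session 12 cannot be derived from the documents. What can be stated is that 12 of 12 VAS ratings from the first session to the last are post-session, and that at the plan's own attrition allowance up to 9.4% of an arm could have a post-session value carried into a home time point. The latter assumes that attrition matches the 3-per-arm allowance and that LOCF is applied as written. The power figures rest on assumed off-session response rates and serve only to show that the added comparisons are supportive.

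This is a cheap improvement worth making before session 12 of the first subject, because the arrival rating cannot be recovered later.

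**What to change.** Leave the primary endpoint, sample size and visit schedule as they are, and make four changes:

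1. Add one VAS on arrival at the visit for procedure 12, before treatment, on its own sheet and under the protocol's existing rule on rescue medication before a VAS.
2. Pre-specify the same 30% responder comparison by Fisher's exact test on that arrival rating and on the 2-week, 4-week and 3-month home VAS. Use the same baseline as the primary analysis, label the comparisons supportive, and report each difference with a 95% interval.
3. State that a post-session rating is not carried forward into any of these off-session time points. Report the number missing by arm, and pre-specify how missing values are handled.
4. Report these results next to the primary result.

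The cost is one extra mark at an existing visit and a little more analysis. The arrival mark might slightly anchor the post-session mark. It would be taken in both arms, and removing the first sheet before the second is given should limit this.
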